8.7. Randomization and Blinding

[figure not shown]
There is no randomization in this study. Matching placebo capsules will be administered during the placebo period so that subjects will be blinded. The investigator, pharmacy, and study clinicians will not be blinded; however, the site personnel involved with conducting imaging procedures and/or interpretations will not be informed regarding treatment period associated with corresponding imaging procedures. Sponsor personnel will not be blinded.

8.8. Concomitant and Excluded Medications

For the duration of the study, subjects must agree to remain on their stable fibromyalgia treatment plan established prior to study participation. Stable is defined as treatment with medication(s) and/or intervention(s) at the same prescribed dose established at least 14 days prior to study drug dosing.

[figure not shown]

[figure not shown]
Breakthrough pain may be treated with NSAIDs or acetaminophen; however, use of NSAIDs or acetaminophen 24 hours prior to study visits that include imaging is prohibited.

[figure not shown]

[figure not shown]
Concomitant medications used within 30 days prior to dosing and through the follow-up visit must be documented in the source documents and on the corresponding electronic case report form (eCRF).

[figure not shown]
9. STUDY ASSESSMENTS AND PROCEDURES

[figure not shown]

[figure not shown]

[figure not shown]

5

1

2

43

9.5. Safety and Pharmacovigilance

9.5.1. Adverse Events – Relationship to Study Drug

An AE is any untoward, undesired, unplanned clinical event in the form of signs, symptoms, disease, or laboratory or physiological observations occurring in a human being participating in a clinical study with an Aptinyx IP, regardless of causal relationship. A “pre-existing” condition is one that is present before study drug dosing and is reported as part of the subject’s medical history. Pre-existing conditions should be reported as an AE only if the frequency, intensity, or character of the pre-existing condition worsens during the course of the study.

Laboratory abnormalities are not considered AEs unless they are associated with clinical signs or symptoms, or require medical intervention. However, a laboratory abnormality (e.g., a clinically significant change detected on clinical chemistry, coagulation, hematology, urinalysis) that is independent from the underlying medical condition and that requires medical or surgical intervention, or leads to IP interruption or discontinuation, must be considered an AE.

For each reported AE, an investigator must assess the relationship to study drug using the following scale:

Unrelated

- Does not follow a known response pattern to the suspect study drug (if response pattern is previously known).
- Can clearly be explained by the known characteristics of the subject’s clinical state or other modes of therapy administered to the subject.

Unlikely Related

- The temporal sequence from dosing of the study drug suggests that a relationship is unlikely.
- Follows a response pattern that is unlike that of the suspect study drug (if response pattern is previously known).
- Could be reasonably explained by the subject’s clinical state or other modes of therapy administered to the subject.

Possibly Related

- Follows a reasonable temporal sequence from dosing of the study drug.
- May follow a known response pattern to the suspect study drug (if response pattern is previously known).

- Could also be reasonably explained by the subject's clinical state or other modes of therapy administered to the subject.

Probably Related

- Follows a reasonable temporal sequence from dosing of the study drug.
- Could not be reasonably explained by the known characteristics of the subject's clinical state or any other modes of therapy administered to the subject.
- Is confirmed by improvement on stopping or slowing dosing of the study drug, if applicable.

When an assessment is not provided, the event will be treated as Possibly Related for purposes of regulatory reporting.

9.5.2. Recording Adverse Events

A "pre-existing" condition is one that is present before study drug dosing and is reported as part of the subject's medical history. Pre-existing conditions should be reported as an AE only if the frequency, intensity, or character of the pre-existing condition worsens during the course of the study. Adverse events will be collected from the time the informed consent is signed to the end of the subject's participation in the study.

Subjects should be instructed to report all potential AEs to the investigator, and, queried in a non-leading manner, without specific prompting (e.g., "How are you feeling?"). The site study staff should assess emerging symptoms of dissociative reaction similar to those caused by NMDA antagonists including memory impairment, disturbance in time, body or environmental perception, stilted speech, emotional withdrawal, impaired coordination, motor retardation, bizarre reasoning or illusory experiences in any sensory perception, or confused state; such symptoms may be captured as AEs.

To avoid vague, ambiguous, or colloquial expressions, all AEs should be recorded in standard medical terminology rather than in the subject's own words. Each AE will also be described in terms of duration (start and stop date), severity, relationship to IP, relationship to study procedure, action(s) taken, and outcome. Diagnoses (rather than symptoms) should be recorded wherever possible.

9.5.3. Reporting Adverse Events

All AEs must be documented, evaluated, and reported in the source documents and eCRF. Adverse event collection begins after the subject has completed the informed consent and continues until the subject's participation in the study ends. Ongoing adverse events should be followed to a satisfactory resolution in the investigator's opinion. Subjects should be instructed to report all AEs to the investigator. In addition, the investigator should seek to elicit any clinical or objective reactions by specific questioning (e.g., "How have you been feeling?") and as appropriate by examination. Information on all AEs should be recorded on the eCRF. All clearly related signs, symptoms, and results of diagnostic procedures performed in relation to an AE should be grouped together and recorded as a single diagnosis.

9.5.4. Severity of Adverse Events

All AEs will be assessed for severity, using the following general grading scale:

Mild: Transient or mild discomfort (< 48 hours); no medical intervention/therapy required.

Moderate: Mild to moderate limitation in activity – some assistance may be needed; no or minimal medical intervention/therapy required.

Severe: Marked limitation in activity, some assistance usually required; medical intervention/therapy, required hospitalization possible.

Life threatening: Extreme limitation in activity, significant assistance required; significant medical intervention/therapy required, hospitalization or hospice care probable.

When changes in the severity of an AE occur more frequently than once a day, the maximum severity for the experience that day should be noted. If the severity category changes over a number of days, then those changes should be recorded separately (with distinct onset dates).

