12.6.1. Adverse Events

A treatment-emergent AE (TEAE) is defined as an AE with an onset that occurs after receiving study drug, or a continuing AE diagnosed prior to the date of first dose of study drug, which increases in severity after the start of dosing. Adverse events will be categorized by system organ class and preferred term with the Medical Dictionary for Regulatory Activities.

Summary tables for TEAEs will include numbers and percentages of subjects experiencing TEAEs by system organ class and preferred term. If a subject has more than 1 TEAE that codes to the same preferred term, the subject will be counted only once for that preferred term. Similarly, if a subject has more than 1 TEAE within a system organ class category, the subject will be counted only once in that system organ class category.

The following TEAE summaries will be provided for each study period (placebo, NYX 2925 20 mg, NYX-2925 200 mg, and follow-up:

- Overall summary of TEAEs,
- TEAEs by system organ class and preferred term,
- Drug-related TEAEs by system organ class and preferred term,
- TEAEs by system organ class, preferred term, and severity.

Serious TEAEs, and TEAEs leading to study drug discontinuation will be identified.

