4.6 Analyses Changes from the Protocol

In Section 12.6.1 of the protocol, it states that TEAE summaries will be provided separately for each study period and the follow-up period. TEAEs will be summarized and grouped based on the last study drug treatment the subject received compared to the start date of the event explained in [Section 5.2](#). The rest of the analyses stated in the protocol support the analyses planned in this SAP.

5. General Statistical Principles

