12.1 Adverse Events

Treatment-emergent adverse events (TEAEs) will be those occurring during or after administration of the first dose of study drug until 30 days after the final dose of study drug. The date and time of first dose of study drug was not collected on the CRF for all subjects. Therefore, the following algorithm will be used to determine if the adverse events are treatment-emergent without a date and time of first dose of study drug:

- Earliest Possible AE Start Date \geq Day 1 (Baseline) Visit and Study Drug Dispensation **and**
- Latest Possible AE Start Date \leq 30 Days After the Final Dose of Study Drug

AEs that started prior to first dosing of study drug, but become worse in severity after receiving study drug will be considered treatment-emergent. The determination of whether or not an adverse event is classified as “treatment emergent” (i.e. TEAE) is not determined by the classification of “relationship

to study drug" collected on the CRF, but rather by the temporal relationship of the adverse event to the administration of study drug.

A related study drug TEAE is defined as any TEAE with at least a possible relationship to the study drug as assessed by the investigator or that is missing the assessment of causal relationship whose relationship to the study drug could not be ruled out. Relationships of "possibly related", "probably related", or missing are collected on the CRF, then those adverse events will be considered related study drug TEAEs. If the "unrelated" or "unlikely related" are collected on the CRF, then those adverse events will be considered not related study drug TEAEs.

Severity is assigned to each adverse event collected on the CRF. Maximum severity has the following order: "life threatening", "severe", "moderate", and "mild" as possible collection options on the CRF. A missing severity will be treated as "unknown" for analysis purposes.

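### Severity changes, including improvement, are recorded with their own onset dates and AEs are assigned to periods by start date, so an AE that only eases can be counted again under a later treatment

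*Protocol*

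**What the plan says.** **Recording.** Protocol 9.5.4 says of a severity category that changes from one day to another: "then those changes should be recorded separately (with distinct onset dates"). The one exception concerns several changes within a day, for which "the maximum severity for the experience that day should be noted". Protocol 9.5.2 adds that "Adverse events will be collected from the time the informed consent is signed", so records can exist before Day 1.

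**Treatment-emergent status.** Protocol 12.6.1 counts "an AE with an onset that occurs after receiving study drug", and also a continuing pre-dose AE "which increases in severity after the start of dosing". SAP 12.1 turns the first part into a date rule: the start date must fall on or after the Day 1 visit and dispensing, and no later than 30 days after the final dose. It then adds: "AEs that started prior to first dosing of study drug, but become worse in severity after receiving study drug will be considered treatment-emergent".

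**Treatment column.** SAP 4.6 states: "TEAEs will be summarized and grouped based on the last study drug treatment the subject received compared to the start date of the event". SAP 5.2 also assigns AE records by start date relative to the Week 2, 4 and 6 visits; some of its treatment labels are redacted. SAP 5.3 adds a pooled column for all NYX-2925 doses in the AE tables.

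**Counting.** SAP 12.1 counts a subject once per system organ class and preferred term, gives results by treatment, and tabulates the total number of events in the overall summary.

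**The concern.** Each rule is reasonable alone; the difficulty lies in combining them. A recording convention meant to preserve the course of an AE creates rows with later onset dates, and the SAP reads onset dates as the time when an event emerged.

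The columns of the TEAE tables are successive treatment periods in the same subjects, always in the order placebo, 20 mg, 200 mg. A row created because an AE is resolving can therefore fall under a different treatment from the one on which the AE began. Carry-over of this kind can add placebo-onset AEs to the NYX-2925 columns, and 20 mg-onset AEs to the 200 mg column, but cannot run the other way. Safety is the secondary objective, and the by-period TEAE summary is its main comparison with placebo.

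**Working it through.** The plan states no figure on this point, so there is none to reproduce. The check applies the written rules to example records.

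**Inputs**
- Target visit days from SAP 5.5.1: Week 2 = 14, Week 4 = 28, Week 6 = 42.
- Last dose on day 42 (assumption), so the TEAE window closes on day 42 + 30 = 72.
- Planned enrolment of about 24 subjects (SAP 4.3).
- The example courses are illustrative assumptions.

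**Rules applied.** A row is a TEAE if 1 ≤ start day ≤ 72. Its column is the treatment being received on its start day. For comparison, the linked approach keeps one row per episode, dated at first onset, and adds a later row only on worsening.

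| Course of the AE | Rows as split | TEAE rows as written | TEAE rows if linked |
|---|---|---|---|
| A: moderate on day −3, mild on day 5 | day −3 (no treatment), day 5 (placebo) | 1, in placebo | 0 |
| B: moderate on day 10, mild on day 17 | day 10 (placebo), day 17 (20 mg) | 2, one each in placebo and 20 mg | 1, in placebo |
| C: severe on day 10, moderate on day 17, mild on day 31 | day 10 (placebo), day 17 (20 mg), day 31 (200 mg) | 3, one in each column | 1, in placebo |

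Nothing worsens in any of these courses.

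**Does another rule remove the extra rows?**
- Counting a subject once per term works within a treatment column. In course B the subject is still counted under placebo and again under 20 mg.
- The total-event count has no such rule: 2 instead of 1 in course B, 3 instead of 1 in course C.
- The worsening clauses add AEs that began before dosing. They do not exclude an improved row whose own onset date falls after dosing. They also concern only AEs from before the first dose. Placebo counts as study drug (Protocol 12.3), so they do not reach an AE carried from placebo into an NYX-2925 period.

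**Size.** Increase in a later column for one preferred term = 100 × k/24, where k is the number of subjects carried over and not already counted there.
- k = 1: 100 × 1/24 = 4.2 points
- k = 2: 100 × 2/24 = 8.3 points
- k = 3: 100 × 3/24 = 12.5 points
- k = 5: 100 × 5/24 = 20.8 points

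The documents give no AE rates, so k is an assumption throughout.

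**The case against.** The strongest reply is that the protocol never calls a severity change a new event. It speaks of changes in one AE being recorded separately, and the SAP refers to the start date of the event, not of a severity segment. Protocol 9.5.2 describes each AE by one start and one stop date. If every severity row were a separate AE, the worsening clauses would be redundant, because a worsened row would already start after Day 1. On that reading an episode keeps its original onset.

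This argument shows a real tension about intent, but it does not settle the derivation. The recording rule expressly asks for distinct onset dates, the SAP works from start dates, and no visible text says which of several dates is the start of the event. For AEs that begin on placebo there is not even a worsening clause to indicate intent.

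Other points stand in part:
- A linking rule could sit in the CRF instructions or table shells, which were not available. The finding is therefore conditional on the rows being unlinked. SAP 12.1, where the derivation is defined, shows no link.
- Protocol 9.5.1 and 9.5.2 treat a condition present before dosing as pre-existing and reportable only on worsening. That weakens the pre-dose case, although the same section collects AEs from consent.
- The study is a small, unpowered pilot with descriptive safety analysis, and all AEs are listed by subject, so a careful reader could trace a grade change. This limits the consequence but does not correct the tables.

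A reader might infer that incidence and event counts are wrong in every period. The documents do not support that: the tables are affected only if such episodes occur and stay unlinked. Nor do all misplaced events move into the NYX-2925 columns. A pre-dose AE that improves in the first two weeks inflates the placebo column. Changes within a day are not split at all.

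**Conclusion.** The concern holds in conditional form. As written, the protocol's recording rule and the SAP's date rules together count an AE that began on placebo and only eased later as a further TEAE under NYX-2925, both by subject and in total events. For carried-over AEs the direction is systematic, because the treatment order is fixed. For pre-dose AEs, the same rules conflict with the stated intent that only worsening counts, and the excess falls mostly in the placebo column.

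The effect is 4.2 percentage points per affected subject for a given term, or 4.2 to 20.8 points over the assumed range of 1 to 5 subjects. This rests on 24 subjects in the column, on the subject having no other event of that term there, and on no linking rule existing elsewhere. No hypothesis test or error rate is involved. It should be corrected because it biases the by-period comparison on the secondary objective and the remedy is cheap.

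**What to change.** Keep the recording rule and change the derivation:

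1. Give each severity record an identifier that links it to its parent AE.
2. In SAP 12.1 and 5.2, set treatment-emergent status and treatment period from the parent's first onset date.
3. Count a later record as a TEAE in a new period only if its severity exceeds the maximum reached before that period; for pre-dose AEs, the maximum before the first dose. A test of any increase within the period would not be enough, because a moderate–mild–moderate course would count as new without ever exceeding its earlier level.
4. Count each linked episode once in total events, and keep all severity records in the subject listings.

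The cost is a parent-event identifier or a linking step in the AE data, plus a short SAP addition. If the CRF instructions already link the records, the SAP need only say so and state which onset date applies.

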9.5.5. Action Taken for Adverse Events

For each reported AE, an investigator must document the action taken according to the following criteria:

- No action taken
- Concomitant medication taken
- Hospitalization or prolongation of hospitalization
- Discontinued study
- Nondrug therapy
- Other (specify)

The investigator must also document the action taken in regards to IP (as a result of a given AE) according to the following criteria:

- Dose not changed
- IP interrupted
- IP withdrawn
- Not applicable
- Unknown

9.5.6. Outcome for AEs

[figure not shown]
AEs should be followed until resolution. For each reported AE, the investigator must document the outcome according to the following criteria:

- Fatal
- Not recovered/not resolved
- Recovered/resolved

- Recovered/resolved with sequelae
- Recovering/resolving
- Unknown

9.5.7. Serious Adverse Event (SAE) Reporting

SAEs are reported to the sponsor-designated medical monitor using the Aptinyx provided form by email or fax at:

An SAE is any AE occurring at any dose that results in any of the following outcomes:

- Death: “Death” is an outcome and is NOT the AE. In the event of death, the cause of death should be recorded as the AE. The only exception is “sudden death” when the cause is unknown.
- Is a life-threatening experience: Life-threatening AEs include any adverse drug experience, which, in the view of the investigator, places the subject at immediate risk of death from the reaction as it occurs. It does not include a reaction that, had it occurred in a more serious form, might have caused death.
- Requires inpatient hospitalization or prolongation of existing hospitalization
- Results in a persistent or significant disability/incapacity: Disability is defined as a substantial disruption in a person’s ability to conduct normal life functions.
- Results in a congenital anomaly/birth defect
- Additionally, important medical events that may not result in death, be life threatening, or require hospitalization may be considered an SAE when, based upon appropriate medical judgment, they may jeopardize the subject and may require medical or surgical intervention to prevent one of the outcomes listed previously. Example: allergic bronchospasm requiring intensive treatment in an emergency room or at home.

All SAEs that result in death or are life threatening, regardless of causal relationship, must be reported to the sponsor-designated medical monitor within 24 hours of the site’s knowledge of the event. A copy of the initial SAE report must be received within 1 business day.

All other SAEs or other events reportable to the United States Food and Drug Administration (FDA) and/or institutional review board (IRB) will be forwarded to the sponsor designated medical monitor within 1 business day.

The SAE report should provide as much of the required information as is available at the time. The following minimum information is required for reporting an SAE: subject identification, reporting source, and an event outcome. Supplemental information may be transmitted using a follow-up report and should not delay the initial report. Aptinyx may contact the investigational site to solicit additional information or to follow-up on the event.

If there is any doubt whether the information constitutes an SAE, the information will be treated as an SAE for the purposes of this protocol. Serious AE reporting will begin at the time of consent and will end 30 days after the last dose.

All relevant documentation pertaining to an SAE (additional laboratory tests, consultation reports, discharge summaries, postmortem reports, etc.) will be provided to the sponsor-designated medical monitor in a timely manner. Serious AEs will be followed until resolution or return to Baseline (when worsening of a pre-existing condition is reported). If an SAE does not return to Baseline but reaches a stable situation that is not expected to change, this may be documented on the SAE form.

9.6 Other Reportable Events

Reports of overdose (with or without an AE), abuse, dependency, inadvertent or accidental exposure, pregnancy, and unexpected therapeutic benefit should be forwarded in the same time frame as an SAE. Overdose occurs when a subject is dosed or has taken a dose greater than the intended or scheduled dose specified by the protocol. All pregnancies occurring during the study must be followed for information regarding the course of pregnancy, delivery, and condition of the newborn. Follow-up should be provided by the investigator to the sponsor-designated medical monitor in a timely manner. When the newborn is healthy, further follow-up is not necessary.

[figure not shown]
